3.3. SAMPLE SIZE: SCHOOL CHILDREN

Considering a seroprevalence of 6.0% (the highest seroprevalence at present reported among the Belgian general population (17)) an effective sample size of 400 would give us margin of error (half the confidence interval width) as a measure of precision of 2.3%. As seen in Figure 1, we gain some precision by increasing the sample size to 1000 but the difference is only 0.8%. Taking in to account the cost, we considered using a sample size of 400 for this study acceptable. Figure 1 shows both the exact binomial confidence interval and the asymptotic version (normal approximation) because we are potentially dealing with low numbers/prevalence, in which case we should not use a normal approximation.

For operational and practical reasons we opted for cluster sampling, choosing 41 clusters from 4,498 Belgian primary schools and 41 clusters from 1,590 Belgian secondary schools. We assume a design effect of 2 will be largely sufficient to account for variability in SARS-CoV-2 prevalence among children in Belgian primary and secondary schools. Thus we required 19.51 subjects per cluster, which we rounded upwards to 20 subjects. This gives us a necessary total number of 820 children to be recruited/examined per age group.

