3.7. DATA ANALYSIS

The analysis will be descriptive for the primary objective. Variables will be described as proportions with a 95% Confidence Interval (95%CI). Several epidemiological parameters/effect measures will be calculated with a 95%CI.

Among others:

- Seroprevalence of SARS-CoV-2: number of children/ number of school staff in whom specific SARS-CoV-2 antibodies was detected by ELISA / total number of children/staff tested.
- SARS-CoV-2 seroconversion rate: Number of children/ number of school staff in whom presence of specific antibodies was detected by ELISA during any of the follow-up tests with a previous sample showing no specific antibody / total number of children/staff followed-up with a baseline negative serum sample, during the study period of 7 months.
- Cumulative incidence
- Incidence rates (using both the total population and the population excluding the non-susceptible from the prior sero-survey testing period)
- Proportion of asymptomatic cases
- Proportion of symptomatic episodes amongst positives versus negatives

A flow diagram of the participants will be created reflecting number of participants approached, eligible and included. The statistical analysis will account for the small differences in sampling probability due to the study design by using specialized procedures for complex (survey) sampling..

For the secondary objectives, uni- and multivariate analysis will be performed assessing risk, protective and predictive factors associated with sero-positivity among children and among staff. Relative risk of sero-positivity in function of specific risk factors (prior to analysis a directed acyclic graphs (DAG) will be constructed and risk factors will be analysed using Poisson regression and effect

measures will be re-calculated and presented as absolute risks and risk differences with their CI). Models will be assessed for presence of confounders and interaction.

When tables will be presented e.g. test positives versus test negatives at the end of the study, no p-values will be presented comparing differences in basic characteristics to avoid chance-findings.

A sensitivity analysis will be performed to estimate bias resulting from the imperfect accuracy of serology testing. If needed other sensitivity analysis will be performed and selection bias will be assessed. Depending on the amount of missing data imputation will be used.

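### Section 3.3: the children's 2.3% margin matches the normal approximation, not the exact interval (2.46%), and the 0.8-point gain at n = 1000 should read 0.9

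*Combined protocol and SAP*

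**What the plan says.** Section 3.3 (sample size, school children) starts from "Considering a seroprevalence of 6.0" per cent and an effective sample size of 400. It reports a "margin of error (half the confidence interval width) as a measure of precision of 2.3" per cent. It then compares this with a larger sample: "we gain some precision by increasing the sample size to 1000 but the difference is only 0.8" per cent. With cost also named as a consideration, 400 is accepted.

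The same paragraph says of the supporting figure: "Figure 1 shows both the exact binomial confidence interval and the asymptotic version (normal approximation"). The reason given is "because we are potentially dealing with low numbers/prevalence, in which case we should not use a normal approximation". The paragraph does not say which of the two methods produced the printed 2.3 and 0.8.

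The next paragraph of section 3.3 turns 400 into a recruitment number: "We assume a design effect of 2 will be largely sufficient", with 41 schools per age group and 20 children per school, or 820 children per age group.

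**The concern.** The paragraph names two interval methods, cautions against one of them at low numbers or prevalence, and then gives a single unlabelled margin. A reader would reasonably take that margin to be the exact one. If it is the normal-approximation value, the precision quoted for the primary outcome is slightly better than the interval the paragraph favours would give. The gain from 400 to 1000 matters for the same reason: the margin and the gain are the only quantitative support in section 3.3 for stopping at 400, and an understated gain makes the smaller sample look a little more attractive than it is.

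**Working it through.** **Inputs**
- Seroprevalence p = 0.06, effective n = 400, comparison n = 1000, and the margin defined as half the interval width: section 3.3.
- Confidence level 95%, two-sided. Section 3.3 does not restate it. It is taken from section 3.7: "Variables will be described as proportions with a 95% Confidence Interval (95%CI").
- Methods: normal approximation and exact binomial, both named in section 3.3. Exact is taken as Clopper-Pearson.

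**Step 1. Reproduce the printed figures (normal approximation)**

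Half-width = 1.96 × √(p(1 − p)/n).
- n = 400: 1.96 × √(0.06 × 0.94/400) = 1.96 × √0.000141 = 2.327%, printed as 2.3%.
- n = 1000: 1.96 × √(0.06 × 0.94/1000) = 1.96 × √0.0000564 = 1.472%, or 1.5% rounded.
- Gain before rounding: 2.327 − 1.472 = 0.855 points.
- Gain from rounded margins: 2.3 − 1.5 = 0.8, the printed value.

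**Step 2. Exact binomial (Clopper-Pearson)**

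For x positives among n, the lower limit is the 2.5% quantile of Beta(x, n − x + 1) and the upper limit is the 97.5% quantile of Beta(x + 1, n − x).
- n = 400, x = 0.06 × 400 = 24: 3.882% to 8.796%, half-width (8.796 − 3.882)/2 = 2.457%. The interval is asymmetric: 2.12 points below 6% and 2.80 points above.
- n = 1000, x = 60: 4.610% to 7.656%, half-width 1.523%.
- Gain: 2.457 − 1.523 = 0.934 points.

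**Step 3. Compare**

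| Quantity | Printed | Normal | Exact |
|---|---|---|---|
| Half-width, n = 400 | 2.3% | 2.33% | 2.46% |
| Half-width, n = 1000 | not given | 1.47% | 1.52% |
| Gain, points | 0.8 | 0.86 | 0.93 |

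- Margin: exact minus normal = 2.457 − 2.327 = 0.13 points. The ratio is 2.457/2.327 = 1.056, so 5.6% wider.
- Gain: 0.9 to one decimal under either method. The 0.8 is therefore a rounding error and not a consequence of the choice of interval.

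**Step 4. Does it reach further?**
- Recruitment: 400 × 2/41 = 19.51 per school, rounded to 20, and 20 × 41 = 820. Neither step uses the margin.
- Realised effective size: 820/2 = 410. The exact half-width there is 2.43%, still not 2.3%.
- Staff (section 3.4, 10% and n = 400, printed 3% and 1%): normal 2.94% with a gain of 1.08, exact 3.06% with a gain of 1.15. Both methods round to the printed values, so the staff paragraph is unaffected.

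**The case against.** The best reply has four parts.

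- **The caution is conditional.** It says that low numbers are potentially an issue and explains why the figure carries both intervals. At the design point 24 positives are expected (400 × 0.06), where many would accept the normal approximation. This stands. A reader might infer that the plan forbids the approximation outright and then breaks its own rule, but the text does not go that far. What remains is an unlabelled margin next to a caution about the method that yields it.
- **The source of 2.3% is inferred.** The document does not name it, and Figure 1, said to show both intervals, cannot be seen in the text available, so a reader of the full document may already have the exact value. This also stands. Some methods the paragraph does not mention also round to 2.3% (Jeffreys 2.33%, for example). The inference is limited to the two methods that are named, and of those only the normal one fits.
- **Nothing downstream depends on it.** Cost was part of the decision, no precision target is set, and section 3.7 plans survey procedures for the analysis rather than a simple binomial interval on 400. Uncertainty in the design effect is of similar or greater weight: the exact-to-normal ratio equals moving the design effect from 2 to 2 × 1.056² = 2.23. This stands and keeps the point minor.
- **The 0.8 is only rounding.** Correct, but it remains wrong to one decimal under both named methods.

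**Conclusion.** The point holds as a small reporting error in two parts. First, the printed 2.3% agrees with the normal approximation (2.33%) and not with the exact half-width of 2.46% (95% CI 3.9% to 8.8%), an understatement of 0.13 points or 5.6% if the exact interval is the intended one. Second, the printed gain of 0.8 points should be 0.9 whichever method is meant (0.86 normal, 0.93 exact).

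This rests on a 95% two-sided level carried over from section 3.7, on Clopper-Pearson as the exact interval, and on attributing 2.3% to one of the two named methods by numerical match.

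Three stronger readings are not supported:
- A reader might infer that the sample is too small. Holding the exact half-width to 2.3% would take an effective n of about 454 (908 children, about 22.1 per school), but the plan reports 2.3% as a result and does not set it as a target.
- A reader might infer that both figures are errors of method. Only the margin depends on the method.
- A reader might set 2.457 against the printed 2.3 and call the interval 7% wider. That compares an unrounded value with a rounded one. Like for like it is 5.6%.

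**What to change.** Either of two edits to section 3.3 is enough.

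- **Preferred:** state that an effective sample size of 400 gives an exact 95% half-width of 2.46% (3.9% to 8.8%) and that 1000 gives 1.52%, a gain of 0.93 percentage points calculated before rounding. The note on rounding is needed because subtracting the two-decimal margins gives 0.94. Margins rounded to one decimal (2.5 and 1.5) would appear to give 1.0 and would repeat the present fault.
- **Alternative:** keep 2.3%, label it as the normal-approximation value, and change the gain from 0.8 to 0.9.

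The cost is one or two figures and a label in a single paragraph. The effective sample of 400, the 20 children per school, the 820 per age group, the staff figures in section 3.4 and the planned analysis are all unchanged.

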3.4. SAMPLE SIZE: STAFF

Considering a seroprevalence of a least 10.0% (the latest number reported among the Belgian blood donors was approximately 4% REF; the seropositive rate increased two to 3 fold in both blood donors and leftover samples in April 2020, i.e. starting two weeks after the lockdown was initiated in March) an effective sample size of 400 would give us margin of error (half the confidence interval width) as a measure of precision of 3%. As seen in Figure 1, we gain some precision by increasing the sample

size, but the gain in precision is moderate (e.g. the margin of error decreases only 1% when $n = 1000$). Taking into account the cost, we considered using a sample size of 400 for this study acceptable. Figure 1 shows both the exact binomial confidence interval and the asymptotic version (normal approximation) because we are potentially dealing with low numbers/prevalence, in which case we should not use a normal approximation. The proposed number of 400 staff members allows to detect a change in sero-prevalence over time in the same persons of approximately twice the margin of error with a power of at least 70%, and a twofold difference in prevalence in two equal sized groups (e.g. primary vs secondary school) with a power of approximately 80%.

These numbers apply to the total study population (staff of primary and secondary school), but they will be stratified according to type of school (and province, social background of the school/pupils). In addition, since we will recruit staff members in schools (10/school) and the condition under study is an infectious disease we assume there will be clustering of observations. While the effect of clustering on the standard errors is not yet known, it is common to assume a design effect of two. For a cluster size of 10 (staff/school), this corresponds to an intracluster correlation (icc) of 0.11.

Because of operational reasons we will recruit school staff in the same schools as pupils, meaning the same 41 primary and the same 41 secondary schools. Considering the above sample size calculation this will give us 410 staff in primary and 410 staff in secondary schools.

[figure not shown]

Figure 1: Expected margin of error by prevalence

3.5. SAMPLING PROCEDURE

Children and staff will be recruited in the same schools.

The study uses a two stage cluster sampling design with geographical and socioeconomic stratification:

- **1st stage: Selection of schools (within province selection of clusters; distribution of clusters per province proportional to number of schoolchildren per province; selection probability of schools proportional to the number of pupils)**

To select the children and staff to be included in the sample, we select 41 clusters for each age group (primary and secondary school children).

First a number of clusters is assigned to each of the 10 Belgian provinces and Brussels-Capital Region proportional to the number of children attending primary or secondary (first grade) education (data from Fédération Wallonie-Bruxelles and Vlaamse Gemeenschap; retrieved June 2020), but with a cap of 5 clusters for more populous provinces and 4 for less populous provinces. This gives us per age group per province and for Brussels-Capital Region following results:

Province	Number of clusters/schools	Proportion residents 6 – 18 years	Number of arrondissements
Antwerp	5	16.1	3
Limburg	4	7.1	3
East Flanders	5	12.8	6
Flemish Brabant	4	10.5	2
West Flanders	4	9.4	8
Hainaut	5	12.2	7
Liège	4	9.8	4
Luxembourg	1	2.8	5
Namur	2	4.6	3
Walloon Brabant	2	3.9	1 (27 municipalities)
Brussels-Capital Region	5 (4F; 1N)	11.2	19 (municipalities)
Total:	41		

Due to capping 3 clusters were removed from the provinces of Antwerp, 2 from East Flanders, and 1 from Hainaut, West Flanders, and Flemish Brabant. Final weights for the calculation of nationwide or regional prevalence estimates will be based on the distribution children by province of residence according to the most recent data from Statistics Belgium (Statbel, 1/1/2020). The total number of clusters per age group is 23 schools from the Vlaamse Gemeenschap, and 18 schools in total from the Fédération Wallonie-Bruxelles and the German-speaking Community.

To ensure both a geographic dispersion and social stratification within province, we will further assign the clusters using a random starting point and fixed increment factor in an ordered list (population size) of arrondissements² (larger arrondissements can be selected more than once), or geographically grouped clusters of municipalities (Walloon Brabant; Brussels Capital Region). A “social-demographic quantile” will be assigned at random to each cluster such that the sum of these quantiles is 1 (e.g. a quartile when 4 clusters are selected in the province). Schools within the geographical region (arrondissement or geographical cluster) will be assigned a similar socio-demographic quantile based on their social index (data available from the Communauté Française and AGODI, Vlaamse Gemeenschap) and number of pupils. One secondary and one primary school will be selected at random within the assigned socio-demographic quantile (if needed, backup schools will be selected at random within the same quantile). The social classification of schools is based on publicly available data, the number of pupils is publicly available for the

² For the selection of primary schools it may seem more reasonable to select municipalities, but not all municipalities have a secondary school.

Flemish schools. and will be requested from the responsible agency for the schools from the federation Wallonie-Bruxelles and the German-speaking Community.

- **2nd stage: Selection of children and staff in each school (convenient sampling in each cluster)**

A local study contact will be identified for each participating school. Eligible groups of pupils (classes) will be identified within the school (randomized if applicable), and all children and their parents/legal caregivers from the selected classes will be informed about the study. Children from whom a parent returns the signed informed consent and who agree themselves (assent) are eligible for enrolment in the study. If consent is obtained from more than 20 children, a random selection of 20 children will be drawn using a simple procedure with a mobile app.

Staff will be informed about the study. Staff who return a signed informed consent are eligible for enrolment in the study. If more than 10 staff members are willing to participate, a random selection of 10 staff members will be drawn using a simple procedure with a mobile app.

3.6. DATA COLLECTION

The selected schools will be contacted by the research assistant (one research assistant for the FR and one for the NL schools) to explain the protocol and obtain their approval. This will be done with the knowledge and involvement of the local CLB (Centrum voor Leerlingen Begeleiding) and PSE (Promotion de la Santé à l'Ecole) units. If approval is given, the schools will choose the eligible classes, taking in to account the guidelines provided by the research team.

3.6.1. Data collection procedure

Biological sample (saliva swab) and survey questionnaire data will be collected simultaneously in ~~October~~ December 2020 (Baseline), ~~January~~ February 2021 (M4 M3) and April/May 2021 (M7 M6) and for primary school pupils: September 2021 (M9) and December 2021 (M12). Each of these testing periods should extend for a maximum of four weeks. In each school, one contact person will be designated to support the study locally and communicate with the researchers. This person will also help in informing the participants and provide and collect the informed consent for each of the participants.

3.6.2. Questionnaire

Demographic, socio-economic, risk-behaviour and ~~child~~ infection and control behaviour related data and COVID-19 clinical symptomatology and illness episodes will be collected using a questionnaire at each testing period. Demographic and socio-economic data will only be collected by the baseline questionnaire. Every testing period, information on COVID-19 related symptoms and illness and the contact with (possible) COVID-19 cases will be asked. The questionnaires can be found in the appendix. Questionnaires will be available in French and Dutch.

The questionnaire will be transcribed in LimeSurvey (the data is automatically stored at the secured Sciensano server). Both the French and Dutch version of the questionnaire will be piloted and checked for readability and understanding as well as timing. Adjustments in phrasing can be made to improve the completion of the questionnaire. The questionnaire will be completed online (via computer or tablet/smartphone) by the parents or staff, respectively, during each testing period (background information only at baseline), and will include a pseudonymous ~~child~~ identifier to link the questionnaire data to the result of the biological sample taken from the participant (child or staff) ~~child~~. The web-link to the questionnaire will be provided by the study researchers to the parents of the participating child³ and participating staff members. Families without internet access, will be invited by the school to complete the questionnaire on a school computer or will receive a paper questionnaire through the

³ Given that 87% of the Belgian households have an internet connection (federal government economy) we opted to using an online questionnaire, and the questionnaire can also be completed on a smartphone.

school which they can complete and return to the school (under closed envelop). The school will deliver these paper questionnaires to the study researchers who will enter the data in the database.

If questionnaires are missing 1 week after closure of a testing period, a reminder will be sent to the (parents of) participants.

Basic data from the participating schools will be collected. Prior to the different sample periods, the schools will be contacted, periodical school closures and known SARS-CoV-2 outbreaks at the schools will be recorded.

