3.2. STUDY DESIGN

This study will be set up as a prospective cohort study.

Children and school staff will be recruited at the 1st testing period in the participating school. Samples will be taken within a timeframe of maximum 4 weeks for all the participants.

Parents/legal child caregiver and staff will need to complete a questionnaire at each of the testing moments providing basic socio-demographic characteristics (at baseline only) and risk-behaviour and health characteristics including presence of symptoms during the time since the previous testing period (at each of the testing periods). The questionnaire will be completed ~~by a parent of caregiver~~ through a secured online application during the same week as the collection of a saliva sample. ~~from the child.~~

The study will last 12 months. There will be in total 3 testing periods when data and sample collection will be performed for the total study population; in ~~October~~ December 2020 (Baseline), ~~January~~ February 2021 (M3) and April/May 2021 (M6). There will be a 4th and 5th testing period for primary school pupils only: in September 2021 (M9) and December 2021 (M12).

Saliva samples will be sent to the Sciensano laboratory for analysis. Serological test results will be communicated to the child's parent/legal caregiver by a closed letter through the participating school.

Epidemiological data analysis will be performed and reported after each testing period and at the end of the study.

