
Sample result

Participants and parents/legal caregivers of participating children will be informed about the result of their ~~child's~~ serological test after each sampling period. The schools will receive the individual reports under closed envelopes and distribute them to the primary caregivers of the participating children and the participating staff. Informed consent forms and accompanying letters will clearly state that a positive test result only implies that the child has been in contact with the SARS-CoV-2 virus, but that currently no assumptions can be made on protection against COVID-19 disease, unless new convincing scientific data becomes available about protection against re-infection. A contact number will be given in case questions remain regarding the study sample results. Distribution of test results will be done through Sciensano.

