7.3. POTENTIAL DIRECT BENEFITS FOR PARTICIPANTS AND INDIRECT BENEFITS FOR BROADER SOCIETY

The potential benefits are mainly indirect as the data collected will help improve and guide efforts to understand the SARS-CoV-2 pandemic and partially the transmission dynamics in the paediatric population and among school staff. Participants will also receive the test results, unless they do not wish to receive these.

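### The questionnaire reminder waits until a week after the whole testing period closes, and nothing keeps it ahead of the result letters, so late respondents may report symptoms knowing that round's antibody result

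*Combined protocol and SAP*

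**What the plan says.** Four timing statements bear on this point.

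- **Intended completion.** Section 3.2 has parents and staff complete the online questionnaire "during the same week as the collection of a saliva sample". It covers risk behaviour and health, "including presence of symptoms during the time since the previous testing period", and section 3.6.2 adds contact with possible cases.
- **Length of a round.** Section 3.6.1: "Each of these testing periods should extend for a maximum of four weeks".
- **Reminder.** Section 3.6.2: "If questionnaires are missing 1 week after closure of a testing period, a reminder will be sent". The protocol describes no other reminder.
- **Results.** Section 3.6.3 says that participants and parents learn the result of the "serological test after each sampling period". On the route it says: "The schools will receive the individual reports under closed envelopes and distribute them to the primary caregivers of the participating children and the participating staff". The only stated exception is the participant's own choice, in section 7.3: "Participants will also receive the test results, unless they do not wish to receive these".

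The symptom reports feed two analyses listed in section 3.7: the proportion of asymptomatic cases and "Proportion of symptomatic episodes amongst positives versus negatives". The only masking stated is that of the laboratory technician (section 3.6.3). The information-bias list in section 6 covers misclassification, imperfect test accuracy and precision. It does not mention reporting influenced by knowledge of the result.

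**The concern.** Symptoms and contacts are recalled over the interval since the previous round, by the parent or by the staff member. Someone who has just learned that the sample was positive may search memory harder for a cough or a sick contact. Someone told it was negative may discount the same event. If so, the error differs by serostatus. The asymptomatic proportion would tend to be understated and the contrast between positives and negatives widened, and a larger sample would not remove this.

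A respondent who answers in the sampling week cannot yet know that round's result. One who answers only after the reminder might. The plan neither orders the two mailings, nor holds a result until that round's questionnaire is in, nor sets a cut-off for late questionnaires, nor separates late answers in the analysis.

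**Working it through.** The plan states no figure on this point, so there is none to reproduce. The check is one of sequence, followed by an illustration of size.

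**1. Lag from sample to reminder** (sections 3.6.1 and 3.6.2)

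- Sampled on the last day of the period: 0 + 7 = 7 days.
- Sampled on the first day of a four-week period: 28 + 7 = 35 days.

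The range is therefore about 1 to 5 weeks, against an intended lag within the same week. Section 3.6.4 expects fieldwork to take 2 to 3 weeks. On that schedule the upper end is 14 + 7 = 21 to 21 + 7 = 28 days.

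**2. Order of the two events**

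| Event | Earliest time under the plan | Condition attached |
|---|---|---|
| Reminder | 1 week after the period closes | questionnaire still missing |
| Result letter | after the sampling period, no date | none, apart from the participant's opt-out |

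Both fall after closure. The letters may precede, accompany or follow the reminder; the text is compatible with all three.

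**3. Illustration of size**

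Inputs from the documents: 820 children per age group and an assumed seroprevalence of 6.0% (section 3.3). Expected positives: 820 × 0.06 = 49.2.

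Inputs that are assumptions, because the documents give neither:

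- the share *L* of positives who answer after seeing the result, 5% to 30% (49.2 × 0.05 = 2.5 to 49.2 × 0.30 = 14.8 children);
- the rise *d* in symptom reporting caused by knowing a positive result, 10 to 30 percentage points.

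Bias in the symptomatic proportion among positives = *L* × *d*:

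- low end: 0.05 × 0.10 = 0.005, or 0.5 points;
- high end: 0.30 × 0.30 = 0.09, or 9 points.

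The asymptomatic proportion is understated by the same amount. If 50% of positives and 30% of negatives truly had symptoms (also assumed) and reporting by negatives did not change, the ratio would move from 0.50/0.30 = 1.67 to between 0.505/0.30 = 1.68 and 0.59/0.30 = 1.97. Any suppressed recall among negatives would add to this and is not quantified here.

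**4. Comparison with sampling error at one round**

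Half-width of the 95% interval for a 50% proportion in 49.2 positives:

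- without clustering: 1.96 × √(0.25 / 49.2) = 0.140, about 14 points;
- with the plan's design effect of 2: 1.96 × √(0.25 × 2 / 49.2) = 0.198, about 20 points.

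Even the high end of the illustration lies below both.

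**The case against.** The strongest reply is that the overlap may never occur. Letters need carrier collection twice a week, a medium-throughput ELISA and sealed reports handed out by schools, for up to 1,640 + 820 = 2,460 participants in a full round. Letters that follow the reminder fit the text at least as well as letters that precede it. This stands. A reader might infer that late respondents do know their result when they answer; the documents do not support that, because no letter date is given. What remains is that the order is left open.

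Second, recall is not blind elsewhere either. Known prior infection does not exclude participation (section 3.1), and anyone positive in one round knows it in the next, however promptly they answer. This also stands. A reader might infer that reordering the mailings would make symptom reporting blind. It would not; the point is confined to people who first learn their status from that round's letter before answering.

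Third, letter dates and the handling of late forms might be set in the operating procedures or the data analysis plan that the protocol promises (sections 3.6.4 and 5), and section 3.7 allows further sensitivity analyses if needed. That is possible, but the protocol names neither an order nor this analysis.

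Fourth, this is the July 2021 amendment. Rounds 1 to 3 were scheduled for December 2020 to April/May 2021, so a new reminder date can reach only rounds 4 and 5, in primary pupils. This is correct and limits the fix.

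**Conclusion.** The point holds as a minor one. The reminder is tied to closure of the whole period instead of to the participant's own sample, and no rule places it, or the questionnaire, ahead of the result. Reporting after disclosure is therefore permitted, though not certain. The results exposed are secondary: the asymptomatic proportion, the symptom comparison by serostatus, and analyses that use reported contacts. Seroprevalence, the primary outcome, does not depend on the questionnaire and is unaffected.

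The size cannot be derived from the documents. A reader might take the 0.5 to 9 points above as an estimate of bias; it is not, because both inputs are assumed. The direction is likewise an expectation about recall, not something the documents show. At one round the effect is probably smaller than sampling error. It deserves attention because it would be systematic and is cheap to avoid.

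**What to change.** **Rounds 4 and 5.** Send the reminder about one week after each school's own sampling visit, and before any result letters for that round are dispatched. This shortens recall for schools sampled early; for a school sampled on the last day the reminder date does not change. Some people will still answer after their letter, so the flag below is needed as well.

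**All rounds for which dates exist.** Compare the completion date (online submission date, or return date for paper forms) with the letter dispatch date. Flag questionnaires completed after dispatch, and repeat the symptom and contact analyses without them as a prespecified sensitivity analysis. Because schools hand out the letters, dispatch precedes receipt, and the flag will include some people who had not yet read their result. Report how many are flagged, by serostatus.

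**Cost.** A separate reminder date for each school in place of one common date, letters held until the last school's reminder has gone out, and one additional analysis. That analysis has slightly fewer questionnaires, possibly selected on responsiveness, and draws on an already small group of positives. It should therefore stand beside the main analysis and not replace it.
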